7.4. Storage

Sites are to store IP supplies in a secure area until dispensed. GLPG3970 200 mg tablets and matching placebo tablets should be stored at room temperature (below 30 °C), should not be refrigerated or frozen and should be protected from light and stored in the original packaging.

Sites will be required to monitor the storage temperature by using at least a min-max temperature-recording device and to keep a minimum to maximum temperature log, which must be completed each working day in order to establish a record of compliance with these storage conditions. The investigator will instruct subjects on how the IP should be stored at home. Storage conditions to be taken into account by the subject when taking IP home, are described in the patient leaflet.

7.5. Treatment Compliance and Drug Accountability

The investigator should discuss treatment compliance with the subject prior to the start of the study. Missed doses should be discussed to try to ascertain the reason(s). Every effort should be

made to ensure the proper subject dose. Subjects with poor compliance will be retrained by the site. IP administration as indicated by the subject (amounts as well as periods) will be recorded on the CRF.

The pharmacist or designated clinical study staff will maintain documentation of the total amount of IP received at the site, amount dispensed to the subject, and the amount of IP returned by the subject to the site. IP supplies for each subject will be inventoried and accounted for throughout the clinical study. At the end of the treatment period, these records will be checked against the inventory by the study monitor. All clinical supplies will be stored in locked and access controlled facilities. Subjects will record IP administration at home in a subject diary.

Subjects will return any unused IP and empty IP packages at each study visit and/or ED visit. Upon sponsor approval, all unused IP and used and/or empty IP packages are to be returned from the sites and/or any vendor involved in the clinical study supplies management activities to the agreed location (depot), if possible. All returns and destructions must be properly documented.

8. CLINICAL STUDY ASSESSMENTS

Every effort should be made to ensure that CSP-required tests and procedures are completed as described in the Schedule of Activities (see Section 8.11). To avoid inter-observer variability, every effort should be made to ensure that all safety and efficacy evaluations are completed by the same individual who made the initial baseline determinations. In case study assessments are not performed for reasons related to SARS-CoV-2 pandemic restrictions, this should be documented in the medical records and CRF.

In case a randomized subject is not able to attend a scheduled study visit on site because of SARS-CoV-2 travel restrictions, a phone call or a televisit may be conducted. It is strongly recommended to conduct planned study assessments for the applicable visit as per protocol as much as possible. If possible and if local regulations allow and the subject agrees, trained study staff or trained personnel are encouraged to collect study assessments at the study subject's home or a local facility if social distancing and hygiene rules can be applied.

Only staff trained in conducting the protocol planned assessments are authorized to perform home or local facility visit assessments and the alternative arrangements need to be adequately documented. Subjects presenting with signs and symptoms of infection, including SARS-CoV-2 infection should immediately contact the site investigator, who should inform the sponsor's medical responsible as soon as possible, and SARS-CoV-2 testing should be performed.

8.1. Timing of Assessments

The study assessments described below will be performed at time points as specified in the Schedule of Activities in Section 8.11. At Visit 1, 4, and 5, subjects need to come for the study visits in a fasting state (no food intake for at least 8 hours).

ICF needs to be signed before any study procedure, including screening procedure, is carried out.

The sequence of study assessments during the treatment period(s) will preferably be as follows when planned at the same time point:

1. Patient Questionnaires (ESSPRI, [REDACTED])
 2. Investigator Questionnaires (ESSDAI, [REDACTED])
 3. 12-Lead ECG
 4. Vital signs
 5. Blood sampling for clinical laboratory assessments and PK [REDACTED]
 6. [REDACTED]
 7. [REDACTED]
 8. [REDACTED]

The following collection time windows apply:

- Vital signs and physical examinations: predose.
 - 12-Lead ECGs (see also Section 8.5.5):
 - Visit 1: 1 triplicate ECG predose and at 4.5 hours postdose
 - Visit 1: 1 single ECG at 1.5 hours postdose and at 3 hours postdose
 - Other visits: single ECGs, see Schedule of Activities in Section 8.11
 - Blood and urine sampling for clinical laboratory safety: any time predose, on the same visit day.
 - Blood sampling for PK determination of GLPG3970:
 - Visit 1: within 30 minutes predose, 1 sample within [0.5-1.5 hours postdose], 1 sample within [2-2.5 hours postdose], and 1 sample at 4.5 hours postdose, immediately after the triplicate ECG
 - Visit 2, 3, and 5: within 30 minutes predose
 - Visit 4: within 30 minutes predose, 1 sample within [0.5-1.5 hours postdose], and 1 sample within [2-2.5 hours postdose]. If the postdose samples could not be collected at Visit 4, they should be collected at Visit 5. It is important that the PK [REDACTED] samples are collected on the same day.

8.1.1. Retesting During Screening

During the screening period, 1 retest of the following assessments is allowed:

- For resting heart rate (after at least 5 min supine position) and blood pressure.
- For QuantiFERON –TB Gold test with indeterminate result (the subject is not eligible if retest result is indeterminate or positive).
- During screening or later during the study, retesting (resampling) of clinical laboratory safety tests or SARS-CoV-2 RT-PCR tests is allowed once and only for technical or transport reasons (e.g. sample hemolyzed, out of stability, late arrival at laboratory impacting sample quality, loss, or destruction of the sample before analysis).

8.1.2. Rescreening of Subjects

If a subject is a screening failure, it is allowed to rescreen the subject once, if the reason for failure is temporary and expected to resolve, as judged by the investigator. When a subject is rescreened, the subject needs to be reconsented and all screening assessments need to be repeated. The subject will be assigned a new subject number. The time in between 2 screening attempts could vary depending on the screening failure reason.

The following data will be collected for screening failure subjects: ICF signed data, demographics, failed inclusion or exclusion criteria, and AEs.

8.2. Unscheduled Visits

Additional visits can be performed at other time points for any safety assessments, if clinically indicated. These unscheduled visits and outcomes of additional assessments need to be recorded in the source and, if it is a CSP-specified assessment performed before the subject's last visit per CSP, also in the CRF.

8.3. Subject and Disease Characteristics

Subjects will be asked to attend the site for a screening assessment. After giving written informed consent, demographic data (year of birth, age, sex, ethnicity, and race) will be collected and a medical history will be taken, including pSS disease history. pSS disease history will capture at least the duration of disease, clinical symptoms, and medication used to treat the disease. A physical examination will be performed, including measurement of weight and height. The subject's diagnosis of active pSS will be confirmed based on the pSS classification criteria described by the ACR-EULAR(10).

Vital signs (systolic and diastolic blood pressure, heart rate, oral/tympanic body temperature, the same method of measuring body temperature to be used throughout the study) will be measured and a 12-lead ECG will be recorded. Subjects should rest for at least 5 minutes in the supine position before the ECG recording, blood pressure, and heart rate measurement.

The inclusion and exclusion criteria will be checked to assess eligibility for the study based on the screening assessments. At Visit 1 (Day 1), it is the responsibility of the investigator to confirm that each subject remains eligible for the study, based on the available data (including data from Visit 1 [Day 1]), before randomization and first IP dosing.

8.4. Efficacy Assessments

8.4.1. EULAR Sjögren's Syndrome Disease Activity Index (ESSDAI) Score

The ESSDAI is a systemic disease activity index to assess 12 domains (i.e. organ systems: constitutional, lymphadenopathy, glandular, articular, cutaneous, pulmonary, renal, muscular, peripheral nervous system, CNS, hematological, biological) in patients with pSS, where each of the domains is divided into 3-4 levels of activity. These scores are summed across the 12 domains in a weighted manner to provide the total score (range 0-123). A clinically meaningful reduction from baseline (≥ 3 points) indicates the improvement of symptoms. ([Appendix 7](#)) (13).

8.4.2. EULAR Sjögren's Syndrome Patient Reported Index (ESSPRI) Score

The ESSPRI is a patient self-reported outcome measure to assess dryness, limb pain, fatigue, and mental fatigue, where each of the domains normally reported as 0 (not at all) to 10 (extremely severe). The final ESSPRI score is the average of 3: dryness, pain, and fatigue. A clinically significant reduction from baseline (at least 1 point or 15% of the baseline value) indicates the improvement of symptoms. ([Appendix 8](#)) (13).

[REDACTED]

8.4.4. [REDACTED]

[REDACTED]

8.4.4.1. [REDACTED]

[REDACTED]

8.4.4.2. [REDACTED]

[REDACTED]

8.4.4.3. [REDACTED]

[REDACTED]

8.5. Safety Assessments

This section describes methods and timing for all safety assessments and recording. Additional assessments (e.g. unscheduled clinical laboratory tests or extra vital signs recordings) are allowed to ensure appropriate collection of safety data and to assess any perceived safety concerns.

8.5.1. Adverse Events

The AEs reporting period for safety surveillance begins when the subject signs the ICF and ends at his/her last FU visit. Investigators are not obliged to actively seek SAEs after the CSP-defined FU period. However, if the investigator is informed about an SAE that occurs at any time after

the subject's post-treatment FU visit and the event is deemed related to the use of IP, they should promptly document and report the event to the sponsor by using the SAE form.

Detailed definitions, reporting period, ratings and reporting requirements for AEs and SAEs are found in Section 11.

8.5.2. Clinical Laboratory Evaluations

The following clinical laboratory safety tests will be performed:

– **Hematology:**

Hematocrit, mean corpuscular volume, mean corpuscular hemoglobin, mean corpuscular hemoglobin concentration, hemoglobin, red blood cell (RBC) count, white blood cell count, white blood cell differential count (absolute and relative), RBC differential count/morphology (if indicated), and platelets.

– **Coagulation:**

INR, activated partial thromboplastin time, and prothrombin time.

– **Clinical chemistry:**

Glucose, fasted glucose, fasted insulin, hemoglobin A1c, urea, creatinine, bicarbonate, uric acid, sodium, potassium, calcium (total), reflex calcium (free/ionized only if serum calcium total is elevated), chloride, phosphorus/phosphate, AST, ALT, GGT, total bilirubin, alkaline phosphatase, alkaline phosphatase bone fraction (if total alkaline phosphatase elevated), creatinine phosphokinase, total immunoglobulin (Ig) levels, lactate dehydrogenase, albumin, total proteins, triglycerides, total cholesterol, high-density lipoprotein (HDL), low-density lipoprotein (LDL), HDL/LDL ratio, high sensitivity C-reactive protein (hsCRP), lipase, and amylase.

Homeostatic model assessment of insulin resistance (HOMA-IR) and HDL/LDL ratio will be derived from clinical chemistry parameters. An estimate of the creatinine CL based on the serum creatinine level will be calculated.

– **Urinalysis:**

Dipstick: pH, glucose, proteins, blood, leukocytes, ketones, calcium, phosphate, and creatinine.

Microscopic examination of the sediment for cellular elements (cylinders, erythrocytes, leukocytes), if indicated.

– **Serology/blood:**

HBsAg (if positive, confirmed by HBV deoxyribonucleic acid [DNA] polymerase chain reaction [PCR]), HCV antibody (if positive, confirmed by reflex HCV RNA), and HIV 1 and 2 antibodies at screening. Positive hepatitis and HIV results should be reported by the investigator as required by local law.

FSH test for females at screening to confirm menopause, if applicable.

– **Pregnancy test for females:**

Serum beta human chorionic gonadotropin at screening (all females), urine pregnancy test (UPT) and urine dipstick (WOCBP only) at Visit 1 (Day 1 predose), at Visit 2 (Day 8 predose), at Visit 3 (Day 29 predose), Visit 4 (Day 57 predose), and at Visit 5 (Day 85 predose).

- **QuantiFERON-TB Gold test** to check for latent or active TB (at screening). TB results should be reported by the investigator as required by local law.
- **SARS-CoV-2:**
IgM Immunoassay.
RT-PCR from a nasal swab sample to check for SARS-CoV-2 infection at screening and RT-PCR from a nasal swab sample and serology testing at baseline, and throughout the study as needed (when SARS-CoV-2 symptoms present). The repeat RT-PCR may be performed 2-3 days prior to the baseline visit to allow for results availability prior to randomization. Positive SARS-CoV-2 results should be reported by the investigator as required by local law.

The clinical laboratory evaluations will be performed at visits specified in the Schedule of Activities in Section 8.11 (see also Section 8.1, “[Timing of Assessments](#)”). Reference ranges will be supplied by the central laboratory. Clinical laboratory values outside the normal range will be flagged and clinical relevance will be assessed by the investigator. Only laboratory test abnormalities judged as clinically significant by the principal investigator should be recorded as AEs. At the discretion of the investigator, when following up AEs, additional laboratory parameters may be tested, and additional samples taken.

Blood and urine sample handling and shipment instructions will be provided in a separate laboratory manual.

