5.5. Potential Risks and Benefits

GLPG3970 has been studied in a nonclinical setting (Section 2.1) in GLP studies in rat and dogs for a duration up to 13 weeks, and is being studied in a FIH study (Section 2.2) where the single ascending dose part has been completed up to the dose of 500 mg and the multiple ascending dose part up to 400 mg q.d. GLPG3970. Study GLPG3970-CL-207 is the first study where GLPG3970 is being administered to subjects with active pSS.

[REDACTED]

[REDACTED]

[REDACTED]

In the healthy volunteers part of study GLPG3970-CL-101, single doses of 10 to 500 mg GLPG3970 and repeated doses of 100 mg q.d., 250 mg q.d., 400 mg q.d. GLPG3970 administered for 14 days to healthy subjects were well tolerated. No death or SAE occurred during the study and no TEAEs led to study drug discontinuation. For more details refer to Section 2.2 and the latest version of the IB and its relevant updates/ addenda.

The most important potential risks based on in vitro and nonclinical studies, and the healthy volunteer part of study GLPG3970-CL-101 are: QT prolongation, hemato-lymphoid system toxicity, gastrointestinal toxicity, and risks related to fertility and pregnancy (see Section 2.1). Serious infections, including opportunistic infections and tuberculosis (TB) are also considered important potential risks based on the mechanism of action of the IP.

Specific for severe acute respiratory syndrome coronavirus 2 (SARS-CoV-2) infections, risk minimization measures have been implemented in this protocol, in order to prevent recruitment of subjects with active infection and to allow prompt intervention, in case a subject is presenting with signs and symptoms of SARS-CoV-2 infection.

GLPG3970 has a novel dual mechanism of action, which is intended to restore the balance of the immune system by reducing several mediators of inflammation and by improving immune-regulatory mechanisms that may be impaired in autoimmune diseases such as, for example, pSS, RA, psoriatic arthritis, and inflammatory bowel disease. This may weaken the immune response and can potentially increase subject's vulnerability to develop infections (e.g. opportunistic infections, SARS-CoV-2, etc.). Careful monitoring and reporting of signs and symptoms is therefore required, to enable prompt medical evaluation and pharmacological or clinical intervention.

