6.3.1.1. Female Subjects

Female subjects are considered of non-childbearing potential if they meet one of the following criteria:

- No menses for 12 or more months without an alternative medical cause. A high follicle stimulating hormone (FSH) level in the postmenopausal range may be used to confirm a postmenopausal state in women not using hormonal contraception or hormonal replacement therapy. However, in the absence of 12 months of amenorrhea, a single FSH measurement is insufficient.
- Permanently surgically sterile (bilateral oophorectomy, i.e. surgical removal of ovaries, bilateral salpingectomy, or hysterectomy, i.e. surgical removal of uterus).

All other female subjects are considered to be of childbearing potential (WOCBP) and must use one of the following highly effective methods of birth control prior to the first dose of IP, during the clinical study and for at least 35 days after the last dose of IP:

- Combined (estrogen and progesterone containing) (oral, intravaginal, transdermal) hormonal contraception associated with inhibition of ovulation plus a barrier method.
- Progesterone-only hormonal (oral, injectable, implantable) contraception associated with inhibition of ovulation plus a barrier method.
- Intrauterine device.
- Intrauterine hormone-releasing system.
- Bilateral tubal occlusion.

- Sexual abstinence defined as refraining from heterosexual intercourse during the entire period of risk associated with the study treatments. The reliability of sexual abstinence needs to be evaluated in relation to the duration of the clinical study and the preferred and usual lifestyle of the subject.

Periodic abstinence (e.g. calendar, symptothermal, post-ovulation methods), declaration of abstinence for the duration of a clinical study, withdrawal, spermicides only, and lactational amenorrhea method are not acceptable as methods of contraception.

In case a WOCPB has a vasectomized partner, provided that partner is the sole sexual partner of the WOCPB clinical study participant and that the vasectomized partner has received medical assessment of the surgical success, then she is not required to use an additional form of contraception.

Within these limits, the specific forms of contraception employed are left to the discretion of the subject, the investigator, and/or the subject's physician.

The safety of GLPG3970 during breastfeeding is unknown. Nursing women are not allowed to take part in this clinical study.

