- A detailed assessment of the subject's clinical condition and repeat laboratory tests for liver function test (LFT), including albumin, creatine kinase, total bilirubin (direct and indirect), gamma-glutamyl transferase (GGT), INR, and alkaline phosphatase should be done.
- Further testing for hepatitis A, B, and C, and for autoimmune hepatitis should be done. Other causes of viral hepatitis (cytomegalovirus or Epstein-Barr virus, etc) should be excluded. Liver imaging should be considered.
- Referral to a hepatologist or gastroenterologist should be requested.

Every effort should be made to keep subjects in the study and on treatment. However, the investigator, who may consult the sponsor's medical leader, can consider stopping the study treatment in case of concerns about the subject's safety, serious or severe AEs or worsening of the disease condition, which in the investigator's opinion needs an alternative treatment approach not being covered in the clinical study (e.g. rescue medication).

When study treatment is discontinued, the subject will be requested to complete the assessments of the ED visit and to return for the FU visit. Reason for discontinuation must be documented in the case report form (CRF).

Subjects will be informed prior to clinical study entry that they are allowed to withdraw from the clinical study. At any time and for any reason, a subject's participation in the clinical study may terminate at their request, without prejudice to their future medical care. The subject will be encouraged to share the reason(s) for withdrawal so this can be documented in the source documents, and to complete the ED visit and FU visit for safety assessments, but will not be obliged to do so.

Subjects who withdraw from the clinical study without contact with the site (lost-to-FU) should be contacted by the site so that their health status can be assessed and documented in the source documents. The site should make every effort to understand whether the subject is alive, including checking the medical records and contacting general practitioner or relatives, if necessary. All attempts must be documented in the source documents.

The sponsor has the right to terminate the clinical study at any time and for any reason.

The sponsor and/or investigator will discontinue the study if:

- Judged necessary for medical, safety, regulatory, or other reasons consistent with applicable laws, regulations, and ICH-GCP.

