7.2. Dosage and Administration

GLPG3970 will be provided as a film-coated tablet containing 200 mg of the active pharmaceutical ingredient G1567970 (G1567970 is the compound code for GLPG3970). A dose of 400 mg (2 x 200 mg tablets) q.d. will be taken orally.

At all dosing days, the IP needs to be taken q.d. at approximately the same time every morning in a fed state (together with a meal), except at Visit 1 (Day 1) when the IP will be taken in a fasted state. At Visit 1 (Day 1), breakfast will be provided to the subject 0.5-1 hour after the IP intake and lunch should be eaten 1 hour before or after the ECG measurement at 4.5 hours postdose. Subjects will be instructed to swallow the tablets of GLPG3970 or placebo as a whole with a glass of water and to not chew the drug prior to swallowing. At Visit 1 (Day 1), IP will be administered on site after predose assessments have been completed. At Visit 2, 3, 4, and 5, subjects also need to take their IP on site.

Subjects will receive tablets to take home. Instructions for dosing and storage are incorporated in the IP labels.

If a subject misses a dose (e.g. because he/she forgot to take the medication), he/she should take the missed dose within 12 hours after the planned intake time. If IP is not taken within 12 hours

after the planned time, the missed dose should be skipped. For each dose taken at home, the time, date, and number of tablets taken should be recorded in the subject's diary card.

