8.11. Schedule of Activities

For detailed instructions on the clinical study procedures, please see referred sections and Section 8.1, “Timing of Assessments”.

EVENT	SCREENING PERIOD	TREATMENT PERIOD ¹						FOLLOW-UP PERIOD
		1	2	3	4	5	ED ²	
Study Visit	S	1	2	3	4	5	ED ²	Follow-up Visit
Study Week	-4 to -1	Baseline	1	4	8	12		
Study Day (D) ± Days	-28 to -1	1	8±1	29±2	57±2	85±2	Early treatment discontinuation	28 ± 3 after last IP dosing
Informed consent	✓							
Inclusion/exclusion criteria	✓	✓						
Demographics	✓							
Medical history	✓							
Physical examination	✓	✓	✓	✓	✓	✓	✓	✓
Vital signs	✓	✓	✓	✓	✓	✓	✓	✓
Body weight and height ³	✓	✓	✓	✓	✓	✓	✓	✓

¹ On dosing days, all assessments are to be performed predose, unless otherwise specified.

² Subjects who discontinue treatment early will be requested to return for an ED visit and to return for a FU visit 28 ± 3 days after last IP administration.

³ Height only to be measured at screening.

EVENT	SCREENING PERIOD	TREATMENT PERIOD ¹						FOLLOW-UP PERIOD
		1	2	3	4	5	ED ²	
Study Visit	S	1	2	3	4	5	ED ²	Follow-up Visit
Study Week	-4 to -1	Baseline	1	4	8	12		
Study Day (D) ± Days	-28 to -1	1	8±1	29±2	57±2	85±2	Early treatment discontinuation	28 ± 3 after last IP dosing
12-lead ECG ⁴	✓	Predose, 1.5h, 3h, 4.5h postdose ⁴	Predose	Predose	Predose	Predose	✓	✓
QuantiFERON-TB Gold test	✓							
SARS-CoV-2 RT-PCR test ^{5,6}	✓	✓	As needed					
SARS-CoV-2 serology test ^{5,6}		✓	As needed					
Randomization		✓						
Blood collection								
– Safety (hematology, coagulation, chemistry)	✓	✓ ⁷	✓	✓	✓ ⁷	✓ ⁷	✓	✓
– Safety (HBV, HCV, HIV serology)	✓							

⁴ At Visit 1 (Day 1), triplicate ECGs will be recorded predose and at 4.5 hours postdose. At all other timepoints, single ECGs will be taken.

⁵ RT-PCR from a nasal swab sample at screening and RT-PCR from a nasal swab sample and serology testing at Visit 1 (Day 1), and as needed when subject presents signs and symptoms of SARS-CoV-2 infection.

⁶ SARS-CoV-2 RT-PCR and serology tests can (optionally) be sampled by a nurse at the subject's home 2-3 days before Visit 1 (Day 1).

⁷ Fasted glucose, fasted insulin, and HOMA-IR only at Visit 1, 4, and 5.

EVENT	SCREENING PERIOD	TREATMENT PERIOD ¹						FOLLOW-UP PERIOD
		1	2	3	4	5	ED ²	
Study Visit	S							Follow-up Visit
Study Week	-4 to -1	Baseline	1	4	8	12		
Study Day (D) ± Days	-28 to -1	1	8±1	29±2	57±2	85±2	Early treatment discontinuation	28 ± 3 after last IP dosing
– Pregnancy test serum (all females)	✓							

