Study Week	-4 to -1	Baseline	1	4	8	12		
Study Day (D) ± Days	-28 to -1	1	8±1	29±2	57±2	85±2	Early treatment discontinuation	28 ± 3 after last IP dosing
– Blood samples for PK GLPG3970		Predose  , 0.5-1.5h, 2-2.5h, 4.5h  postdose 	Predose 	Predose 	Predose  , 0.5-1.5h, 2-2.5h postdose 	Predose 	✓	
–								
–								
Urine sample								
– Safety (urine)	✓	Predose	Predose	Predose	Predose	Predose	✓	✓

 At Visit 1, 2, 3, 4, and 5, PK sample to be taken within 30 minutes predose.

 At Visit 1, the PK sample collected at 4.5 hours postdose must be taken immediately after the triplicate ECG.

 At Visit 1, 4, and 5 subjects must come for the study visits in a fasting state (no food intake for at least 8 hours). If the postdose samples could not be collected at Visit 4, they should be collected at Visit 5. It is important that the PK samples are collected on the same day.

EVENT	SCREENING PERIOD	TREATMENT PERIOD 						FOLLOW-UP PERIOD
		1	2	3	4	5	ED 	
Study Visit	S	1						Follow-up Visit
Study Week	-4 to -1	Baseline	1	4	8	12		
Study Day (D) ± Days	-28 to -1	1	8±1	29±2	57±2	85±2	Early treatment discontinuation	28 ± 3 after last IP dosing
- Pregnancy testing (UPT, dipstick) (WOCBP only)		Predose	Predose	Predose	Predose	Predose		
Subject diary evaluation		✓	✓	✓	✓	✓	✓	✓
ESSDAI	✓	✓		✓	✓	✓	✓	
ESSPRI	✓	✓		✓	✓	✓	✓	

EVENT	SCREENING PERIOD	TREATMENT PERIOD 						FOLLOW-UP PERIOD
		1	2	3	4	5	ED 	
Study Visit	S	1	2	3	4	5	ED 	Follow-up Visit
Study Week	-4 to -1	Baseline	1	4	8	12		
Study Day (D) ± Days	-28 to -1	1	8±1	29±2	57±2	85±2	Early treatment discontinuation	28 ± 3 after last IP dosing
Dispense IP		✓	✓	✓	✓			
IP administration 		Once daily throughout the treatment period						
AE and concomitant medication		throughout the study						

[figure not shown]
 At Visit 1 (Day 1), the IP will be administered at the study site in a fasted state. Breakfast will be provided to the subject 0.5-1 hour after the IP intake. Lunch should be eaten 1 hour before or after the ECG measurement at 4.5 hours postdose. At all other dosing days (including Visit 2, 3, 4, and 5), the IP should be taken in a fed state (together with a meal).

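### No pregnancy test is scheduled at the early discontinuation or Follow-up visit, so a woman who stops early can have about four weeks of dosing with no scheduled test after it

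*Protocol*

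**What the plan says.** Protocol section 8.5.2 schedules a serum test for all females at screening. Women of childbearing potential then have urine tests before dosing on Days 1, 8, 29, 57 and 85. The list closes with "Visit 4 (Day 57 predose), and at Visit 5 (Day 85 predose"), and no later visit is named.

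The protocol's own section 8.11 row for the urine test is not in the public text, but SAP Table 1 reproduces the schedule. Its row "Pregnancy testing (UPT, dipstick) (WOCBP only") has entries at Visits 1 to 5 and blanks at ED and Follow-up. The row for safety urine in the same table is ticked at both.

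For a woman who stops treatment early, protocol section 6.4 states that "the subject will be requested to complete the assessments of the ED visit and to return for the FU visit". A footnote to section 8.11 times the second of these: she is asked "to return for a FU visit 28 ± 3 days after last IP administration".

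Protocol section 5.5 counts "risks related to fertility and pregnancy" among the most important potential risks. Section 6.3.1.1 requires contraception "during the clinical study and for at least 35 days after the last dose of IP".

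**The concern.** While treatment continues, each interval between visits ends with a pregnancy test. A woman who stops between visits loses that closing test and is never given another, although she is asked to come back twice. The women whose last stretch of dosing goes unchecked are therefore the early stoppers, many of whom may have stopped for safety reasons.

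Section 11.3.3 requires a pregnancy to be reported within 24 hours and followed to its outcome, but both duties begin only once the pregnancy is known. Without a test at ED or Follow-up, that knowledge depends on symptoms, self-report, open questioning about adverse events, physical examination or a test done at the investigator's discretion. The safety urine collected at both visits does not help, because the dipstick analytes listed in section 8.5.2 do not include hCG.

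At stake is how completely and how early pregnancies exposed to a new drug are identified.

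**Working it through.** The plan states no figure for this gap, so the check is date arithmetic on the schedule.

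**Inputs**
- Urine test days: 1, 8, 29, 57 and 85, all before dosing (protocol section 8.5.2).
- Visit windows: ±1 day at Day 8 and ±2 days at Days 29, 57 and 85 (section 8.11).
- Follow-up: 25 to 31 days after the last dose (28 ± 3, section 8.11).
- Tests precede the dose on visit days: "On dosing days, all assessments are to be performed predose, unless otherwise specified" (section 8.11) and "At Visit 2, 3, 4, and 5, subjects also need to take their IP on site" (section 7.2). A last dose on a visit day therefore follows a test that same day.

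**Formulas**
- Days from last test to last dose = last dose day − last test day.
- Doses since the test = that difference + 1, because the test-day dose comes after the test.
- Days from last test to Follow-up = that difference + 25 to + 31.

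**Results at nominal visit days, last dose the day before the next visit**

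| Last dose | Last test | Test to last dose (days) | Doses since test | Test to Follow-up (days) |
|---|---|---|---|---|
| Day 7 (before Visit 2) | Day 1 | 7 − 1 = 6 | 7 | 31–37 |
| Day 28 (before Visit 3) | Day 8 | 28 − 8 = 20 | 21 | 45–51 |
| Day 56 (before Visit 4) | Day 29 | 56 − 29 = 27 | 28 | 52–58 |
| Day 84 (before Visit 5) | Day 57 | 84 − 57 = 27 | 28 | 52–58 |
| On a visit day, including completers | Same day | 0 | 1 | 25–31 |

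**Maximum with visit windows.** Suppose Visit 3 is on Day 27, Visit 4 would be on Day 59, and the last dose is on Day 58. Then 58 − 27 = 31 days, 32 doses, and 31 + 31 = 62 days to Follow-up.

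**With tests added at ED and Follow-up.** The documents give no window for the ED visit. Assume it takes place x days after the last dose, with x from 0 to 7. In the nominal worst case the longest untested gap is the larger of 27 + x and (25 to 31) − x.
- x = 0: the larger of 27 and 25–31, giving 27–31 days.
- x = 7: the larger of 34 and 18–24, giving 34 days.
- With visit windows: at most 31 + 7 = 38 days.

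The longest gap therefore falls from 52–58 to 27–34 days, or from 62 to 38 with windows.

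**Reach of a Follow-up test.** The contraception period runs to at least day 35 after the last dose, so Follow-up comes 35 − 31 = 4 to 35 − 25 = 10 days before that point.

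**The case against.** The case against accepts the reading and disputes its weight.

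- **The 28-dose figure is an upper bound.** It needs a last dose the day before a booked visit, and the distribution of stopping times is unknown. A woman who last doses on Day 84 is nearly a completer, and the documents do not say whether she would attend as Visit 5, with a test, or as ED, without one. This stands for Visit 5. The same figure arises before Visit 4, where she is plainly an early stopper.
- **The 52–62 days include 25–31 days off drug.** The clearance and embryo-fetal findings are redacted, so the relevance of that part cannot be judged. This stands. The figures are days without a scheduled test and should not be read as days of exposure.
- **A test after the last dose cannot change dosing.** During treatment a confirmed pregnancy stops the drug (section 6.4), whereas here only earlier knowledge is gained. Few cases are expected, since only 20 subjects are planned on active drug. This stands and limits the severity.
- **Other safeguards exist.** Contraception is mandatory, unscheduled tests are permitted, and physical examination and adverse event collection cover both visits. None of these is a scheduled test, so none closes the gap.
- **The Follow-up test is the weaker half.** It precedes day 35, and a completer has already been tested on her last dosing day. This is fair. It would, however, show a conception that was too early to appear on Day 85, which would be at least 25 days old by then.
- **The trial has ended.** SAP section 1 records a recommendation on 26 November 2021 to terminate for liver toxicity, and the study was stopped. An amendment can no longer add tests here. The same event shows that early stopping was a real possibility under this schedule.

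**Conclusion.** The concern holds. The pregnancy test list omits the two visits that an early stopper is asked to attend. At worst this leaves 28 doses (32 with visit windows) with no scheduled test after them, and 52–58 days (62 with windows) from the last test to Follow-up. Stopping earlier in the schedule leaves less, and a last dose on a visit day leaves only the 25–31 days that a completer has.

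The consequence is slower or missed detection of an exposed pregnancy, for a risk the protocol itself ranks as important. It does not add exposure or alter any efficacy conclusion, and few cases are likely. The change should be made because it is easy, with the ED test as the stronger half.

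This rests on the list in section 8.5.2 and the SAP copy of the schedule, since the protocol's own row is not visible. The reduction to 27–34 days also assumes that ED takes place within 7 days of the last dose. The number of women of childbearing potential is not given.

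**What to change.** In protocol section 8.5.2 and the section 8.11 schedule, add the existing urine pregnancy test for women of childbearing potential at the ED visit, as the priority, and at Follow-up. Carry both into SAP Table 1 and the pregnancy listing already planned in SAP section 6.3.2.9. With this trial stopped, the practical use is in any later study that reuses the schedule.

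The cost is one extra test per completing woman of childbearing potential and at most two per early stopper. Even if all 30 planned subjects were such women and all stopped early, that is 30 × 2 = 60 tests. No new visit, urine collection or listing is needed. Section 8.9 sends pregnancy tests to a central laboratory, so the unit cost is that of the method used at Visits 1 to 5, and a cheap site dipstick should not be assumed.

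The downside is an occasional false positive that needs confirmation. A conception shortly before Follow-up, or after it but before day 35, may still be missed.
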